### 6.5. Participating Centers

The study will be carried out in public hospitals with a relevant number of surgeries with general anesthesia. Centers will also be selected based on the distance between OR and

PACU which should not exceed 10 min walking distance. About 10 hospitals will be invited to participate in the study.

# 7. STATISTICAL ANALYSIS

## 7.1. Sample size determination

Sample size determination was calculated by assuming that the Portuguese population to be submitted to elective surgery with general anesthesia is approximately 100.000 cases/year.

From the previous study of [name] et al, the incidence of patients that arrive at the post anesthesia care unit with objective evidence of incomplete neuromuscular recovery was 26%.

When considering this incidence of 26%, a margin of error of 5% (acceptable maximum deviation) and a confidence interval of 95%, we obtained a minimum sample size of 295 patients (StatsDirect 3 Statistical Software).

Considering conservative estimation for the discontinuation rate of 20%, it is expected that approximately 360 patients are required to achieve the primary endpoint.

### 7.2. Primary Endpoint

• TOF ratio < 0.9 at PACU

## 7.3. Secondary Endpoints

- TOF ratio < 0.7 at PACU
- TOF ratio <0.9, TOF ratio <0.7 at PACU by reversal agents administered (neostigmine, sugammadex or none)
- TOF ratio <0.9, TOF ratio <0.7 at PACU by NMB monitoring used intraoperatively

## 7.4. Exploratory Endpoints

• TOF ratio <0.9, TOF ratio <0.7 at PACU by co-morbidities and ASA status

### 7.5. Missing data

Missing data will not be imputed.

### 7.6. Interim Analyses

Not applicable.

## 7.7. Statistical and Analytical Methods

### 7.6.1. Definition of Analysis Population

Full analysis set population (FAS) will include all treated patient if the patient meets the all criteria.

TOF result will be defined as the average of 3 measures. If the 3 measures have a difference above 20%, another sequence of 3 TOF measurements should be assessed.

### 7.6.2. Variables and Statistical Methods

#### Variables/Time Points of Interest

- Demographic/anthropometric information (i.e: age, sex, height and weight)
- Clinical history
- Co-morbidities
- Vital signs (i.e.temperature, oxygen saturation, heart rate and arterial blood pressure)
- ASA classification
- Surgical diagnostic
- Anesthesia duration (time)
- Perioperative medication, its' dosages and last administration time (used during surgical procedure, including neuromuscular blocker and reversal agents)
- Time between date of surgery and date of discharge
- TOF ratio at PACU
- Adverse events
- Assessment if NMB monitoring in the OR during surgery was performed
- Final outcome (discharge or death).

#### Statistical Methods

All subjects that meet the study criteria will be included in the statistical analysis. The TOF result is defined as the average of 3 measures as described in the study procedures.

A descriptive statistical analysis will be performed on all demographic and clinical data. Considering the continuous variables distributions, data will be presented as mean and standard deviation or as median, minimum and maximum, as appropriate. Categorical variables will be presented as absolute and relative frequencies.

Patients will be stratified as follows:

- patients with TOF ratio  $\geq 0.9$
- $\circ$  patients with TOF ratio < 0.9
- $\circ$  patients with TOF ratio < 0.7.

#### Primary Variable

The primary variable of the study is the TOF ratio <0.9. Absolute and relative frequencies will be calculated. 95% confidence intervals will be estimated and presented.

#### Secondary Variables and Exploratory Variables

Comparisons will be performed between TOF ratio <0.9, TOF ratio <0.7 at PACU, and the following variables:

- the use of reversal agents (neostigmine, sugammadex or none)
- NMB monitoring used intraoperatively and type of monitoring used
- o co-morbidities and ASA status

Statistical significance of the comparisons with TOF ratio <0.9 and TOF ratio <0.7 at PACU will be performed through Chi-square test or Fisher's Exact Test. In addition, relative risks and 95% CI for TOF ratio <0.7 and TOF ratio <0.9 at PACU will be performed for the comparisons. All tests will be performed considering a significance level of 0.05 (5%). Analysis will be performed using IBM SPSS Statistics.

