# 1. SYNOPSIS

| Title                      | Incidence of Postoperative Residual Neuromuscular Blockade - A Multicenter,
Observational Study in Portugal.  |  |  |
|----------------------------|--|--|--|
| Study Design               | Epidemiological multicenter, observational, prospective study.   |  |  |
| Primary
Objective       | To determine the incidence of postoperative residual neuromuscular blockade - defined by a TOF ratio < 0.9 - at PACU arrival.  |  |  |
| Secondary
Objectives    | To determine the incidence of severe postoperative residual neuromuscular blockade
– defined by a TOF ratio < 0.7 at PACU arrival   |  |  |
|                            | To evaluate the association of postoperative residual blockade and the use of reversal agents (neostigmine, sugammadex or none)  |  |  |
|                            | To evaluate the association of postoperative residual blockade and the use of intra-
operative monitoring of neuromuscular blockade   |  |  |
| Target
Population       | Subjects aged at least 18 years old (n=360) admitted for different types of elective surgical procedures requiring general anesthesia with neuromuscular blocking agents.  |  |  |
| Sample Size
Calculation | 
 
Sample size was calculated according to the following assumptions:
 
Portuguese population to be submitted to surgery with general anesthesia in the next year is approximately 100.000 cases
 
incidence of patients that arrive at the PACU with objective evidence of incomplete neuromuscular recovery is 26%
 
Discontinuation rate of 20%
 
Assuming a margin of error of 5% and a confidence interval of 95%, it is expected that approximately 360 patients are required to achieve primary endpoint
 
 |  |  |
| Statistical
Analysis    | Patients will be stratified as follows: patients with TOF ratio $\geq$ 0.9, patients with TOF ratio < 0.9, patients with TOF ratio < 0.7   |  |  |
|                            | Absolute and relative frequencies will be calculated for each category of TOF ratios.
95% confidence intervals will be estimated and presented.   |  |  |
|                            | Statistical significance of the comparisons with TOF ratio <0.9 and TOF ratio <0.7 at PACU will be performed through Chi-square test or Fisher's Exact Test. In addition, relative risks and 95% CI for TOF ratio <0.7 and TOF ratio <0.9 at PACU will be performed for the comparisons.   |  |  |

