# 1.1. Study Flow Chart

|  | Pre-
surgery           | Post-surgery                       |  |
|--|---------------------------|------------------------------------|--|
| Procedures   | At
Anesthetic
visit | Period 1
At PACU arrival | Period 2
At hospital discharge |
| Written informed consent   | x                         |                                    |  |
| Inclusion/exclusion criteria   | x                         | x                                  |  |
| Patient number   |                           | x                                  |  |
| Vital signs: arterial blood, pressure,
heart rate, temperature and oxygen
saturation |                           | x                                  |  |
| Neuromuscular blockade assessment
(TOF ratio measurements)                              |                           | x                                  |  |
| Demographic data (gender, age,
weight, height)  |                           | x                                  |  |
| Clinical history   |                           | x                                  |  |
| Co-morbidities   |                           | x                                  |  |
| Information about operating room   |                           | x                                  |  |
| Surgical diagnostic  |                           | x                                  |  |
| ASA status   |                           | х                                  |  |
| Medication: NMBA, NMBA reversal agents, volatile anesthetics, hypnotics, opioids           |                           | x                                  |  |
| Dates: discharge/death   |                           | x                                  |  |
| Adverse events   |                           |                                    | x  |
| Final outcome: discharge/death   |                           |                                    | x  |

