# 4. RATIONALE

General anesthesia is usually achieved through the balance of three components: analgesic, hypnotic and neuromuscular blocking agents (NMBAs). NMBAs optimize surgical conditions and tracheal intubation. Nevertheless, one of the problems associated is the residual neuromuscular blockade, secondary to the remaining effect of these agents at a moment that complete reversal of their effect would be desirable.

Residual neuromuscular blockade is frequently described in surgical patients at the post anesthesia care units (PACUs) when non-depolarizing NMBAs are administered in the operating room (OR). Incidence values range from 16% to more than 70% with a definition of residual neuromuscular blockade in presence of train-of-four (TOF) ratio < 0.7-0.9. The use of NMBAs of intermediate action, intraoperative neuromuscular monitoring and reversal of NMBAs have been described as factors that contribute to the reduction, but not the elimination, of residual neuromuscular blockade.

Quantitative neuromuscular monitoring methods, such as acceleromyography, are the most reliable to assess neuromuscular blockade.8,15 Quantitative neuromuscular monitoring provides a more objective data on neuromuscular transmission and improves detection of residual neuromuscular blockade in comparison with visual or tactile evaluation of the TOF response.

For many years, the standard criterion of adequate recovery of neuromuscular function was a TOF ratio of at least 0.7. However, evidences have been provided that considerable signs and symptoms of residual neuromuscular blockade may persist until a TOF ratio of 0.9. Therefore, presently, the criterion for adequate reversal of residual neuromuscular blockade is a TOF ratio  $\geq$  0.9 at the thumb adductor.

Clinical consequences of residual neuromuscular blockade in PACUs have been documented since 1979. Impaired airway protective reflexes and increased risk for aspiration, a reduced hypoxic ventilator response, pharyngeal dysfunction, hypoxemia, diplopia and unpleasant symptoms of muscle weakness are complications of residual neuromuscular blockade that may increase postoperative morbidity.

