A first study was conducted in eight Portuguese hospitals between July and November 2010 reported a global incidence of 26% of TOF ratio < 0.9 at arrival at the PACU highlighting the dimension of the problem in Portugal.

Since 2010 neuromuscular blockade management had considerably changed. This previous study promoted a growing conscience of the real importance of residual blockade in our surgical patients and convinced us that changes must be done to improve these results. Clinical sessions on neuromuscular blockade management and monitoring were held in various Portuguese hospitals. At the same time, a novel neuromuscular reversal agent (sugammadex) was available and experience with this new drug has been increasing each year replacing in many cases the conventional anticholinesterasic drugs. Based on these two facts we propose to reassess the incidence of residual neuromuscular blockade six years after the first study keeping a similar study design to confirm the paradigm shift that we believe might have happened.

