## 5.2. Secondary Objective

- To determine the incidence of severe postoperative residual neuromuscular blockade
   defined by a TOF ratio < 0.7 at PACU arrival

- To evaluate the association of postoperative residual blockade and the use of reversal agents (neostigmine, sugammadex or none)
- To evaluate the association of postoperative residual blockade and the use of intraoperative monitoring of neuromuscular blockade

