# 6. INVESTIGATIONAL AND ANALYSIS PLAN

### 6.1. Overall Study Design

This is a multicenter, observational/non-interventional study involving adult patients undergoing different types of elective surgical procedures requiring general anesthesia with neuromuscular blocking agents.

The study will have two periods:

- Period 1 Evaluation at PACU arrival.
- Period 2 Collection of hospital patient discharge data.

A total of 360 patients will be included from approximately 10 centers in Portugal, where the PACU is adjacent to the Operating Room (OR). Each center should recruit between 30 and 40 patients.

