### 6.3.1. Period 1 - data collection at PACU arrival

Immediately after patient arrival in the PACU and as soon as clinically adequate (basic monitoring and oxygen therapy in place) the anesthesiologist assigned to the PACU (who was not involved in the anesthetic procedure) will collect demographic data (gender, age, weight, height), vital signs (heart rate, blood pressure, oxygen saturation and temperature). Neuromuscular blockade (TOF Ratio) will be measured. Clinical history, co-morbidities, surgical diagnosis, ASA classification and perioperative medication data (dosage and last administration time) will be collected as well.

As this is an observational study, intra-operative monitoring of neuromuscular blockade will not be mandatory by protocol and will be left at the discretion of the anesthesiologist as according to the clinical practice. Only information about whether this evaluation was performed or not, and if yes if it was used quantitative or qualitative methods, will be collected in the CRF.

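### The reversal-agent and monitoring associations are planned only as one-factor relative risks, not labelled unadjusted, although both exposures are the anesthesiologist's choice and the main co-acting factors are already collected

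*Combined protocol and SAP*

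**What the plan says.** Section 5.2 sets two association objectives besides the incidence of severe blockade. One concerns intraoperative monitoring. The other reads: "To evaluate the association of postoperative residual blockade and the use of reversal agents (neostigmine, sugammadex or none".

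The analysis for both is in section 7.6.2 (Secondary Variables and Exploratory Variables) and is repeated in the Synopsis. Significance testing "will be performed through Chi-square test or Fisher's Exact Test", and "relative risks and 95% CI for TOF ratio <0.7 and TOF ratio <0.9 at PACU will be performed for the comparisons". Each test uses the 0.05 level. Co-morbidities and ASA status appear only as further separate comparisons. Where the plan speaks of stratifying patients (Synopsis, 6.3.1, 7.6.2), it means grouping them by TOF result, which is the outcome. It does not mean a stratified estimate.

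On the exposures, section 6.3.1 leaves intraoperative monitoring to the anesthesiologist's discretion, and section 6.3.3 does the same for drugs and type of monitoring. On what else acts on the outcome, the Rationale says: "The use of NMBAs of intermediate action, intraoperative neuromuscular monitoring and reversal of NMBAs have been described as factors that contribute to the reduction".

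On data, the flow chart (1.1) lists "Medication: NMBA, NMBA reversal agents, volatile anesthetics, hypnotics, opioids". Sections 6.3.1 and 7.6.2 add dosages, last administration times, age, weight, ASA class and whether monitoring was done. For monitoring, section 6.3.1 limits collection: "Only information about whether this evaluation was performed or not, and if yes if it was used quantitative or qualitative methods". Depth of block when reversal was given is not listed.

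**The concern.** Neither exposure is assigned. A patient given one reversal agent may also be more or less likely to have been monitored, to have received a particular blocking agent, or to be in a hospital with particular habits. The protocol itself says that the first two of these matter for residual blockade. A one-factor relative risk mixes them, and nothing in the plan tells the reader so.

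The setting raises the chance of over-reading. The Rationale gives teaching sessions on block management and monitoring, and the arrival of a new reversal agent, as the reasons for repeating the 2010 survey: "Based on these two facts we propose to reassess the incidence of residual neuromuscular blockade six years after the first study". Relative risks for those same two factors, with p-values and no caveat, may be taken as explaining any change in incidence.

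At stake is how two secondary results are interpreted. The primary incidence estimate does not depend on them.

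**Working it through.** **The plan's own figure (section 7.1).** With p = 0.26, margin 0.05 and 95% confidence, n0 = 1.96² × 0.26 × 0.74 / 0.05² = 295.6. The finite-population correction for 100,000 gives 294.8, rounded up to the stated 295. That figure serves the primary incidence. No figure is given for the associations. With 360 enrolled and 20% lost, 360 × 0.8 = 288 are evaluable.

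**A recorded co-factor (inputs assumed).** Monitoring halves the risk. Half the hospitals use monitoring and the agent each in 70% of cases, independently within hospital, and the other half use each in 30%.
- P(monitored | agent) = (0.7² + 0.3²) / (0.7 + 0.3) = 0.58, and P(monitored | no agent) = 0.42.
- Crude RR = true RR × (1 − 0.5 × 0.58) / (1 − 0.5 × 0.42) = true RR × 0.71/0.79 = true RR × 0.90.
- With 80%/20% use the shares are 0.68 and 0.32, and the factor is 0.66/0.84 = 0.79.

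An agent with no effect would thus show 0.90 or 0.79. Adjusting for monitoring restores 1.00 here only because hospital is assumed to act through these two factors alone.

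**Sampling error for comparison.** At 26% incidence the 95% interval around RR 1 is exp(±1.96 × √(2 × 0.74 / (n × 0.26))). For 144 v 144 this is 0.68 to 1.48, and for 96 v 96 it is 0.62 to 1.61. A shift to 0.90 lies well inside both. A shift to 0.79 is also inside, but nearer the limit.

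**An unrecorded factor: block depth (inputs assumed).** Suppose 40% of patients have deeper block (60% risk unreversed), 60% lighter block (15% risk), and a true reversal RR of 0.50. The crude RR depends on who is reversed:

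| Reversed, deeper | Reversed, lighter | Crude RR |
|---|---|---|
| 90% | 50% | 0.97 |
| 80% | 40% | 0.88 |
| 90% | 30% | 1.19 |
| 70% | 70% | 0.50 |
| 50% | 70% | 0.38 |
| 40% | 80% | 0.29 |

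The bias can run either way. In the first three rows, stratifying on a proxy for depth with 80% sensitivity and specificity removes only 23 to 30% of the bias on the log scale.

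**Centre (simulated, inputs assumed).** Take 10 centres of 29 patients, an agent that halves risk, and no true monitoring effect. The crude monitoring RR is about 0.91 (70/30 pattern) or 0.78 (80/20). A random intercept gives about 0.92 or 0.79, removing 4 to 6% of the log-RR bias. If centres also differ for other reasons, the share removed is about 25 to 30% at a between-centre SD of 0.3 in log risk, and about 52 to 68% at 0.6. These are averages of 300 simulated studies and carry Monte Carlo error.

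**Room for adjustment.** Events with TOF ratio <0.9 among 288 patients, at an assumed 10 events per parameter:

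| Incidence | Events | Parameters |
|---|---|---|
| 26% (section 7.1) | 75 | 7 |
| 16% (low end of the range in the Rationale) | 46 | 4 |
| 10% (assumed) | 29 | 2 |

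Reversal has three levels and so takes two parameters. Adding binary monitoring and a two-group blocking-agent term makes 2 + 1 + 1 = 4, which fits at 46 events. Age makes 5, which fits only at the higher count. At 29 events the reversal contrasts alone use the allowance. Per centre, 288/10 = 28.8 patients yield 7.5 events at 26% or 4.6 at 16%, too sparse to stratify by centre.

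**The case against.** The strongest reply is that the objectives ask for association and promise no independent or causal effect. Crude relative risks describe an association correctly, and the Rationale's two reasons are reasons to re-measure incidence, not hypotheses about its cause. All of this stands. What it leaves open is labelling, since nothing in the plan tells the reader that the estimates are unadjusted.

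It can also be said that adjustment cannot remove confounding by indication, that events may be too few, and that a shift of the size illustrated may be hidden by sampling error. The first is right for block depth, though not for monitoring and blocking agent, which are recorded directly. The second is right if incidence has fallen, and the authors hope that practice has improved. The third is right for 0.90. Together these limit the weight of the point and the length of any model.

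A reader might infer more: that the crude results will be wrong by a known amount or in a known direction, that they will favour one agent, or that an adjusted analysis would give a causal effect. The documents support none of this. Every bias figure above rests on assumed inputs, the direction changes with who is reversed, and a main determinant of the choice to reverse is not listed as collected. Nor should a random intercept be presented as removing confounding by centre. It does so only in part, by an amount that depends on how strongly centres differ.

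**Conclusion.** The point holds as a cheap improvement to two secondary analyses, and ranks below an error in the primary analysis. The plan analyses two clinician-chosen exposures one at a time, without calling the results unadjusted, although it names the co-acting factors and collects them. Each crude relative risk can carry those factors and local practice. The amount is unknown: the illustrated 0.90 and 0.79 for a true value of 1.00 depend on the assumed hospital patterns and the assumed halving of risk by monitoring. The incidence estimate is untouched. The conclusion rests on the text alone: no model, covariate or label appears anywhere in the document.

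**What to change.** In section 7.6.2:

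- **Label.** Keep the crude relative risks and call them unadjusted and descriptive. This is the minimum.
- **Adjust, for TOF ratio <0.9 only.** Pre-specify one short adjusted relative risk per exposure, for example by modified Poisson regression with robust variance. For reversal agent (two parameters), enter monitoring and blocking agent (grouped in advance) in fixed order, then age if events allow. For monitoring, enter grouped blocking agent, then age and ASA if events allow. Leave reversal out of the main monitoring model as a possible mediator and add it only as a sensitivity analysis.
- **Centre.** Account for it by a random intercept or a small-sample-corrected cluster variance, and note that a random intercept removes between-centre confounding only in part. Centre is not in the lists of collected variables, but is known in a multicentre study where "Each center should recruit between 30 and 40 patients".
- **Parameter limit.** Fix it in advance, for example at 10 events per parameter (7 at 75 events, 4 at 46, 2 at 29), and count both reversal contrasts. Where the limit leaves no room, and for TOF ratio <0.7, report only crude or penalised results.
- **Limitation.** State that block depth at reversal is not listed as collected, so that adjustment is partial and the results are not causal.

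The cost is SAP wording, slightly more analysis and wider intervals. Apart from the centre identifier, no variable is needed beyond those already listed. At low incidence only the crude results may be supportable.
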